##### 10.5.2 Laboratory Test Results

Laboratory analytes are provided in the protocol Table 13. Summary tables of **selected** chemistry and hematology data and changes from baseline over time will be provided for each protocol scheduled visit by **pooled AMG 986 and pooled placebo treatment groups for part A and part B of the study and by each treatment group for each cohort HFrEF and HFpEF for part C of the study.**

Number and percentage of subjects of each troponin status “undetected”, “detected” and “elevated” at each scheduled assessment may be summarized **in a similar way as laboratory summaries.** Summaries will also be presented treating troponin as a

continuous variable **in a similar way as laboratory summaries**. Troponin values below or above quantifiable limits will be treated as equal to the limits.

### 10.5.3 Vital Signs

Summary tables for all the vital signs parameter data **including blood pressure, heart rate, respiratory rate, and body temperature** and corresponding changes from baseline at each protocol scheduled study visit **by pooled AMG 986 and pooled placebo treatment groups for part A and part B of the study and by each treatment group for each cohort HFrEF and HFpEF for part C of the study** will be provided.

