## **2.4 Risk/Benefit Assessment**

### **2.4.1 Risk Assessment**

AMG 986 has an identified risk of embryo-fetal toxicity and malformations. In developmental and reproductive toxicology studies in rats and rabbits, oral administration of AMG 986 resulted in abortions, embryo-fetal toxicity and external, visceral and skeletal malformations. Women of childbearing potential are not eligible to participate in this study, and male subjects must agree to practice an acceptable method of effective birth control and not donate sperm while on study and through 11 weeks after receiving the last dose of AMG 986. These inclusion/exclusion criteria will mitigate the risk of embryo-fetal toxicity.

AMG 986 has a potential risk of causing changes in blood pressure. Studies have shown that the principal effect of the apelin/APJ system is to counterbalance the renin-angiotension-aldosterone system, and apelin affects vascular tone and blood pressure. AMG 986-related cardiovascular changes in the nonclinical program were limited to modest and reversible decreases in mean blood pressure at the highest IV dose in the rat and small dose-independent increases in mean blood pressure in the anesthetized dog. Subjects will be closely monitored for changes in cardiovascular parameters, such as blood pressure, heart rate, and ECG measurements, and for signs and symptoms suggesting adverse events.

The nonclinical (toxicology and safety pharmacology) package suggests a safe profile for the initiation of clinical trials with AMG 986. Genetic toxicology and photosafety evaluations indicated that AMG 986 is not genotoxic or phototoxic. No AMG 986-related toxicity was identified in the rat or dog toxicology studies that were conducted with oral (6- and 9-months duration in rats and dogs, respectively) or IV (14-day studies) dose administration. The AUC-based exposure margins based on NO(A)EL doses from the rat and dog toxicology studies support the planned oral and IV infusion clinical dose ranges. Additionally, no AMG 986-related effects in the safety pharmacology studies were identified, including data indicating that QTc interval prolongation risk is low.

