#### **6.2.1.3.3 Dose Stopping Rules**

IV or PO dosing will be stopped or modified by the DLRM if suspected adverse drug reactions and/or changes in safety data (including but not limited to vital sign, ECG or clinical laboratory results) are observed and these changes pose a significant health risk in the opinion of either the investigator or Amgen.

No antidote to AMG 986 exists. Standard medical therapies should be used to treat adverse signs or symptoms that do not promptly resolve with discontinuation of the IP.

Investigators must follow patients until the complete resolution of any clinically significant event, irrespective of an IP dosing change.

For subjects receiving IV investigational product the following scheme should be applied in the occurrence of a significant change in blood pressure, heart rate, other vital sign, ECG, laboratory result or any other significant adverse event considered by the

Approved

investigator to be clinically relevant and directly related to infusion of investigational product.

- A change from baseline systolic or diastolic blood pressure levels  $\geq 15\%$  or a change in heart rate  $\geq 25\%$  during infusion should be followed by a 50% reduction of infusion rate for at least 15 minutes.
- If 3 consecutive assessments of blood pressure, heart rate, or other vital signs taken 5 minutes apart are considered to be back to pre-dose levels, restoration of initial infusion rates should be attempted with close monitoring.
- If subsequent assessments show a persistent and significant change in the same vital signs or adverse event considered by the investigator to be related to investigational product, a decision by the investigator can be made to
  - Continue at the reduced rate of infusion.
  - Further reduce infusion rate or stop infusion rate entirely.
- If other clinically relevant adverse event considered by the investigator to be related to investigational product occurs, a decision by the investigator can be made to:
  - Reduce rate of infusion by 50%.
  - Stop infusion rate entirely.

In either case, subsequent assessments, as described above, should guide investigational product administration.

In the event that a change from initial dosing rate is necessary, the Amgen medical monitor should be informed as soon as possible.

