### **10.5 Planned Methods of Analysis**

#### **10.5.1 General Considerations**

Descriptive statistics will be provided for selected demographics, adverse events, vital signs, ECG, PK, selected laboratory measurements, and selected echocardiographic measures. Descriptive statistics on continuous data will include means, medians, standard deviations, and ranges, while categorical data will be summarized using frequency counts and percentages.

Placebo-treated subjects in Part A and separately, subjects in Part B will be combined to form composite placebo groups for each Part. Separate summaries and analyses will be performed for Cohorts in Parts A and B of the study. Placebo-treated subjects in Part C will be separated per cohort (HFREF versus HFpEF). Graphical summaries of the data may also be presented. When data are summarized by time, the values recorded against the scheduled time points listed in the protocol will be used. When assessing minimum/maximum increases or decreases over the study, all assessments, including unscheduled assessments will be used. Unless stated otherwise in the statistical analysis plan, the data analysis will be conducted using subjects in the safety analysis set. For statistical analyses comparing change from baseline, only subjects with both baseline and at least one post-baseline assessment will be included.

Results from the intravenous and from the oral portion of the study will be reviewed separately and together as well in some cases as appropriate.

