#### **10.5.2.1.2 Vital Signs**

Subject-level data for vital signs including blood pressure, heart rate, respiratory rate, and body temperature will be presented and reviewed for each subject. The analyses of vital signs will include summary statistics over time (for each protocol scheduled study visit) by cohort by Part. Depending on the size and scope of changes, summaries of changes from baseline over time may be provided.

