## 10. Statistical Methods of Analysis

### 10.1 General Principles

The primary analysis will occur after the database lock following last subject last visit.

Descriptive statistics will be provided for selected demographics, adverse events, vital signs, ECG, selected laboratory measurements, and selected echocardiographic measures. Descriptive statistics on continuous data will include means, medians, standard deviations (SD), first and third quartiles and ranges, while categorical data will be summarized using frequency counts and percentages.

**AMG 986 and** Placebo-treated subjects in Part A and Part B will be combined to form composite **AMG 986 and** placebo groups, **respectively** for each Part, **wherever appropriate**. . Placebo-treated subjects in Part C will be separated per cohort (HFReF versus HFpEF). Graphical summaries of the data may also be presented.

When data are summarized by time, the values recorded against the scheduled time points (refer to protocol section 7.1) listed in the protocol will be used.

Unless stated otherwise in this statistical analysis plan, the data analysis will be conducted using subjects in the safety analysis set. For statistical analyses comparing change from baseline, only subjects with both baseline and at least one post-baseline assessment will be included.

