### 11. Changes From Protocol-specified Analyses

We have redefined some of the analyses to be by “treatment group” instead of by “cohort” to emphasize the role of the placebos. As **decided by the study team post discontinuation of the study, most of the summaries (except exposure to investigational product) are not presented by cohort levels for each treatment group and are provided by pooled AMG 986 and pooled placebo groups.** In other places we use the wording “study cohort” to emphasize the different dose levels.

To restrict the scope of analysis post the discontinuation of the study earlier than planned, following changes were made in the reporting of results from protocol-specified analysis:

- Subject-level data listings will not be presented and reviewed for vital signs (protocol section 10.5.2.1.2) and ECG (protocol section 10.5.2.1.3),
- Summary of maximum change from baseline in QTcF and QTcB and maximum post-baseline values in QTcF and QTcB as stated in protocol section 10.2.5.2.1.3 will not be provided.
- Analysis of pharmacokinetic endpoints as stated in protocol section 10.5.3.1 will not be performed by the CPMS group.
- Analysis of echocardiographic measures as stated in protocol section 10.5.3.2 will not be performed. The analysis is restricted to HFrEF cohort for Part C of the study for selected parameters of left ventricular systolic function including left ventricular ejection fraction, stroke volume by volumetric (MoD) and Doppler assessment (LVOT). The summary will be based on PD analysis set.

Analysis of exploratory endpoints as stated in protocol section 10.5.4 will not be performed

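### SAP v3.0 leaves unscheduled blood pressure and heart rate readings out of every vital-sign output and plans no per-subject vital-sign result

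*SAP*

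**What the plan says.** Protocol 10.5.1 has two rules. Summaries over time use values at scheduled time points. For extremes, "When assessing minimum/maximum increases or decreases over the study, all assessments, including unscheduled assessments will be used". Protocol 10.5.2.1.2 adds: "Subject-level data for vital signs including blood pressure, heart rate, respiratory rate, and body temperature will be presented and reviewed for each subject".

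SAP 10.1 keeps the first rule: for summaries by time, "the values recorded against the scheduled time points (refer to protocol section 7.1) listed in the protocol will be used". It has no counterpart to the second. SAP 10.5.3 plans tables of the vital-sign values "and corresponding changes from baseline at each protocol scheduled study visit", and nothing else. SAP Section 11, listing the cuts made after early discontinuation, states: "Subject-level data listings will not be presented and reviewed for vital signs". It does not mention the rule on minimum and maximum changes. SAP Section 12 says that no data fall outside the plan.

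SAP 4.1.1 keeps, as a primary endpoint, the incidence of subjects with clinically significant changes in several safety measures, vital signs among them. Protocol 2.4.1 names the matching risk: "AMG 986 has a potential risk of causing changes in blood pressure".

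**The concern.** The protocol generates off-schedule readings when blood pressure or heart rate moves. During IV infusion, a blood pressure change of at least 15% or a heart rate change of at least 25% leads to a rate reduction, and the next step depends on closely spaced checks ("If 3 consecutive assessments of blood pressure, heart rate, or other vital signs taken 5 minutes apart", protocol 6.2.1.3.3). Under protocol 7.2.10, abnormal values may be repeated and the repeats go on the CRF. These readings are collected for a risk that the protocol names, and the report would not show them.

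The second gap is at subject level. The endpoint counts subjects, while the planned tables describe visits. With the listings gone, no vital-sign output follows one subject across the study.

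**Working it through.** The plan states no figure on this point, so there is none to reproduce. The check compares the texts and then looks at schedule coverage.

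**1. Which readings enter which output**

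| Protocol | SAP v3.0 |
|---|---|
| Summaries over time use scheduled time points (10.5.1) | Kept (10.1) |
| Minimum/maximum changes use all readings (10.5.1) | No counterpart in 10.1; not mentioned in Section 11 |
| By-visit statistics; change summaries optional (10.5.2.1.2) | By-visit statistics and changes, both firm (10.5.3) |
| Subject-level presentation (10.5.2.1.2) | Cancelled and declared (Section 11) |

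The by-visit table is the only vital-sign output left. A reading that belongs to no scheduled time point has no place in it. The 5-minute infusion checks are of this kind. A repeat entered under a scheduled time point might be tabulated, but the SAP does not say which value is then used.

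**2. Can a per-subject result be recovered from the by-visit tables?** No. The range at a visit gives the extreme value but not whose it is. The same minimum at four visits could come from one subject or from four.

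**3. Schedule coverage during IV infusion (illustration).** Assume that an episode starts at a uniformly random time and lasts L hours. It overlaps a reading at time t if it starts between t − L and t. The coverage is the combined length of these intervals divided by the infusion length T.

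- Part A IV Cohorts 3 to 5 (protocol Table 10), T = 24, readings at 0.25, 0.5, 1, 1.25, 1.5, 2, 6, 12 and 24 h. For L = 0.25: 9 × 0.25 / 24 = 9%. For L = 2: the readings up to 2 h cover 2 h, and those at 6, 12 and 24 h cover 2 h each, so 8 / 24 = 33%.
- Part B IV (protocol Table 12), T = 96, the same times plus 48, 72 and 96 h. For L = 0.25: 12 × 0.25 / 96 = 3%. For L = 2: (8 + 3 × 2) / 96 = 15%.

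The longest gaps are 12 h and 24 h. Effects in the first 2 h, where sampling is dense, would be caught more often. An episode between scheduled times is seen at all only if somebody takes a reading then.

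**4. Part C (context only).** The vital-signs row of protocol Table 14 has 6 post-dose on-treatment times (1, 2, 6, 172, 337 and 340 h). Adding the ECG times, at which protocol 7.2.10 also calls for blood pressure, gives 11 (4, 170, 174, 338 and 342 h are new). All fall on Days 1, 8 and 15. The other 21 − 3 = 18 dosing days have a scheduled pre-dose reading only.

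**The case against.** Much of the case for the plan stands.

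- A reader might infer an undeclared breach of a promised worst-change table. The documents do not support that. The protocol 10.5.1 sentence is conditional: it says which readings to use if extremes are assessed. Protocol 10.5.2.1.2 promises no such table for vital signs. The maximum-change summary that the protocol does plan is for QTcF, and SAP Section 11 declares that one dropped.
- A reader might infer that only means are planned, so that opposite changes cancel and the tables look flat. SAP 10.1 also specifies medians, SDs, quartiles and ranges. If 3 of 15 patients rose 20% and 3 fell 20% at a scheduled visit, the mean change would be 0, but the range would run from −20% to +20% and the SD would be √(6 × 400 / 14) = 13.1.
- A reader might infer that the lost readings are those most likely to show the effect. The 5-minute checks follow a detected change and a rate reduction, and ask whether values have recovered. The triggering reading may itself be scheduled and so tabulated. The explicit 5-minute rule covers IV dosing only; for oral dosing the extra readings are discretionary repeats.
- The Part C count describes sparse scheduling, which no table can cure.
- Changes reported as adverse events appear in the outputs of SAP 10.5.1. During the study, unblinded dose level review meetings examined vital signs, and protocol Table 8 provides for stopping dosing and convening a meeting after a suspected reaction.
- The reduced scope after early discontinuation is open, and the listing cut is declared.

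What remains is narrower. Adverse event outputs depend on the investigator having called the change an event, and dose level review is not a reported result. Neither replaces a per-subject vital-sign summary in the report.

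**Conclusion.** The point holds as a modest gap in the safety report. Under SAP v3.0, unscheduled blood pressure and heart rate readings appear in no vital-sign output, and no vital-sign table gives a per-subject result for the primary endpoint component on clinically significant vital-sign change.

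No hypothesis test is planned, so no error rate or power is affected. The documents do not give the number of unscheduled readings, so the loss cannot be counted. The IV coverage figures rest on assumed episode lengths of 0.25 to 2 h and a uniform start, and they do not show that any episode was missed. The conclusion also assumes that unscheduled readings are not entered under a scheduled time point.

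**What to change.** In SAP 10.5.3, add one table per Part and treatment group (per cohort in Part C). It should give each subject's maximum increase and maximum decrease from baseline in systolic pressure, diastolic pressure and heart rate over a stated on-treatment window, from all assessments including unscheduled ones. Summarise these by median, quartiles and range, and show the number of readings per subject. Add a short listing of subjects with unscheduled blood pressure or heart rate readings. Carry the protocol 10.5.1 rule into SAP 10.1 to govern the table; restoring that sentence alone, or only declaring its omission in Section 11, would change no result.

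The table supplies subject-level extremes. It is not an incidence of clinically significant change, for which SAP 10.5.3 gives no criterion.

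The cost is one table and one listing beyond the restricted scope, from data already on the CRF. Extremes grow with the number of readings, and subjects under closer watch have more, so the table should be read by arm alongside the reading counts. No dose or clinical rule changes.

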### 10.5.4 Physical Measurements

Subject weight, height and BMI will be presented **as part of baseline characteristics** and reviewed for all subjects.

### 10.5.5 Electrocardiogram (ECG)

Summaries of all ECG parameters and changes from baseline over time will be provided by **pooled AMG 986 and pooled placebo treatment groups for part A and part B of the study and by each treatment group for each cohort HFrEF and HFpEF for part C of the study**. Baseline will be defined as mentioned in [section 6](#). The analysis of Fridericia's (QTcF) QT correction and Bazett's (QTcB) QT correction will be performed for subjects in Part A and Part B using the derived results as specified in [section 6](#).

### 10.5.6 Exposure to Investigational Product

A listing of unique manufacturing lot numbers, and a subject listing of manufacturing lot number will be provided. Additionally an exposure table will be provided with the summaries of number of doses, cumulative doses and average doses for each cohort and treatment group in Part B and Part C.

### 10.5.7 Exposure to Concomitant Medications

**Concomitant medications will not be summarized with the restricted scope of analysis post the discontinuation of the study earlier than planned.**

## 10.6 Pharmacokinetic/Pharmacodynamic Analyses

### 10.6.1 PK Parameters for AMG 986

The pharmacokinetic **endpoints calculation and analyses will not** be performed by the CPMS group **with the restricted scope of analysis post the discontinuation of the study earlier than planned.**

Plasma samples will be analyzed for AMG 986 concentrations using a validated assay **and a listing for individual concentration-time data will be provided by the CPMS**

group. Additionally, CPMS group will also provide plots to present exposure-response relationship for echocardiographic measures of stroke volume and ejection fraction.

#### 10.6.2 Echocardiographic Measures

Echocardiographic parameters of left ventricular systolic function including left ventricular ejection fraction, stroke volume by volumetric (MoD) and Doppler assessment (LVOT) will be summarized along with changes from baseline and relative (percent) changes from baseline for these parameters by treatment group for HFrEF cohort of Part C. Figures will be produced to plot mean and SE of left ventricular ejection fraction and to plot mean relative (percent) change from baseline in left ventricular ejection fraction and stroke volume by volumetric (MoD) and Doppler assessment (LVOT) by treatment group. The summary will be based on PD analysis set.

For the purpose of study data tabulation model (SDTM), echocardiographic data collected from both vendors ICON and BWIC will be utilized for all parts of the study. For analysis data model (ADaM), ICON vendor data will be used for Part A and Part B of the study and BWIC vendor data will be used for Part C of the study.

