### **10.3 Access to Individual Subject Treatment Assignments by Amgen or Designees**

Blinded individuals will not have access to unblinded information until the study is formally unblinded. Amgen staff and their designees involved in the study will not be blinded, but will be given treatment assignments only when there is a need to use the information for analysis discussion and internal decision-making, in particular, when concerning safety issues. Access to treatment assignments and other restricted data are described in Amgen standard documents. Unblinded individuals will ensure the keeping of the blind. Unblinding and potentially unblinding information should not be distributed to the investigators or subjects prior to a study cohort being formally unblinded. An exception is the unblinding of the Principal Investigator or designee who, as a member of the DLRM, will have access to the unblinding DLRM outputs.

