#### **10.5.3.2 Echocardiographic Measures**

Echocardiographic parameters of left ventricular systolic function (left ventricular ejection fraction, stroke volume, wall thickening and end-systolic volume index) and left ventricular diastolic function (E/e' ratio, E-wave deceleration time, and left atrial volume index) in healthy subjects participating in all Parts of the study will be measured and analyzed for changes from baseline. In Part C, additional echocardiographic measures such as ventriculo-arterial coupling and global strain patterns in heart failure patients will be evaluated. Changes from baseline for these parameters will be summarized by cohort and treatment group and by schedule assessment for all Parts of the study. Statistical modeling of a potential dose-response relationship may be pursued for a few key echocardiographic parameters in Part C as appropriate.

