**NCT Number: NCT03276728**

**This NCT number has been applied to the document for purposes of posting on  
Clinicaltrials.gov**

Version Number	Date (DDMMYYYY)	Summary of Changes, Including Rationale for Changes
Original (v1.0)	04 Aug 2016	
[Amendment 1 (v2.0)]	11 Apr 2018	The purpose of SAP amendment 1 was to provide details of the statistical analyses that have been outlined within the Protocol Amendment 7 dated 14 March 2018.
[Amendment 2 (v3.0)]	17 Jun 2019	The purpose of SAP amendment 2 is to align with the Protocol Amendment 8 dated 27 July 2018 and also to limit the scope of analysis due to early discontinuation of the study as referenced in early discontinuation memo dated 15 April 2019. The scope of the analysis is restricted to key endpoints/ parameters, for selected parts/ cohorts of the study in agreement with study team to be used for the purpose of abbreviated Clinical Study Report.

---

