### Secondary Objectives:

- To characterize AMG 986 pharmacokinetics (PK) after IV infusion and oral administration in healthy subjects and heart failure patients.
- To characterize the pharmacodynamic (PD) effects of AMG 986 in healthy subjects and in heart failure patients.

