#### 4.1.2 Secondary Endpoints

- AMG 986 PK parameters including, but not limited to, maximum observed concentration (Cmax), the time of maximum observed concentration (tmax), area under the concentration-time curve (AUC), and oral bioavailability.
- Changes over time from baseline in echocardiographic parameters of left ventricular systolic and diastolic functions (left ventricular ejection fraction, fraction shortening, stroke volume, wall thickening, end-systolic and end-diastolic volumes and indexes, septal and lateral e', E/A ratio, E/e' ratio, E wave deceleration time, left atrial volume index and ventriculo-arterial coupling (Part C only)) in healthy subjects and in heart failure patients.

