### 9.2.1 Echocardiography Data

Echocardiographic data will be collected, tested for quality, and provided by ICON Imaging, Inc. to GSO-DM according to transfer protocols also described in the Data Management Plan. **Due to concerns regarding quality of echocardiographic data from Parts A and B, an additional echo core lab, Brigham and Women's Hospital Research Imaging Core (BWIC), was added to the study on 12th October 2017. While no clinically meaningful inconsistencies were noted upon review of data from both core labs, the precision of measurements from BWIC was noted to be superior and therefore, measurements from BWIC are reported for Part C in lieu of measurements from ICON Imaging while ICON Imaging measurements are reported for Part A and B.**

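### SAP v3.0 keeps the echo endpoint for healthy subjects and heart failure patients but plans change-from-baseline summaries only for HFrEF, and does not say why HFpEF is left out

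*SAP*

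**What the plan says.** The protocol (Section 10.5.3.2) planned echo summaries across the whole study: "Changes from baseline for these parameters will be summarized by cohort and treatment group and by schedule assessment for all Parts of the study".

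SAP v3.0, dated 17 June 2019, keeps the matching objective, "To characterize the pharmacodynamic (PD) effects of AMG 986 in healthy subjects and in heart failure patients". Section 4.1.2 keeps an endpoint of about 15 systolic and diastolic measures, ending "left atrial volume index and ventriculo-arterial coupling (Part C only)) in healthy subjects and in heart failure patients". The PD analysis set (Section 7.4) is not limited to one cohort.

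The version history says the amendment was made in part to "limit the scope of analysis due to early discontinuation of the study". Section 10.6.2 then plans tables and figures for LVEF and for stroke volume by the volumetric (MoD) and Doppler (LVOT) methods, with changes and "relative (percent) changes from baseline for these parameters by treatment group for HFrEF cohort of Part C". Section 11 lists this as a departure from the protocol: "The analysis is restricted to HFrEF cohort for Part C of the study for selected parameters of left ventricular systolic function".

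Three other statements bear on the point:
- Section 9.2.1, on the two core labs, says that second-lab (BWIC) values serve Part C "while ICON Imaging measurements are reported for Part A and B".
- Section 10.6.2 assigns echo data from all three Parts to the analysis datasets.
- Section 10.6.1 promises exposure-response plots for stroke volume and ejection fraction, with no Part or cohort named.

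**The concern.** A retained secondary endpoint should have an analysis, or a statement that it has none and why. Here the endpoint still covers healthy subjects and heart failure patients as a whole, while the planned change-from-baseline output covers one of the two heart failure cohorts and no healthy subjects. Early discontinuation explains a shorter report. It does not explain why one Part C cohort keeps its echo tables and the other loses them.

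Two things are at stake. First, a reader of the abbreviated report could not tell whether HFpEF showed no effect, an unfavourable change, or too few usable echocardiograms to say. Second, the cohort and the measures were chosen late, in a study where unblinded review was routine. Without a stated reason, the HFrEF result carries a doubt about selection that is easy to remove.

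**Working it through.** **Numbers covered.** The documents give no target for the echo endpoint, so the only plan figures to reproduce are the counts in SAP Section 3.2.
- Part A: 11 × 8 = 88. Part B: 8 × 8 = 64. Healthy total: 88 + 64 = 152, as stated.
- Part C: 2 × 20 = 40. Planned total: 152 + 40 = 192.
- On AMG 986 at 3:1: 0.75 × 152 + 0.75 × 40 = 114 + 30 = 144, as stated.

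Planned coverage of the echo tables:
- HFrEF: 20/192 = 10.4%.
- Outside: 152 + 20 = 172, and 172/192 = 89.6%.
- On AMG 986 and outside: 144 − 15 = 129, and 129/144 = 89.6%.

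Protocol Section 2.4.1 gives actual numbers at 01 June 2018: 116 + 38 = 154 healthy subjects and 12 heart failure subjects, 166 in all. The HFrEF/HFpEF split of the 12 is not given. If all 12 were HFrEF, (166 − 12)/166 = 92.8% fall outside the tables; if none were, 100% do. Final enrolment is not in the documents.

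**How the same SAP treats HFpEF elsewhere.**

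| SAP section | HFrEF | HFpEF |
|---|---|---|
| 10.2 to 10.4 accountability, deviations, baseline | by treatment group | by treatment group |
| 10.5.1 adverse events | by treatment group | by treatment group |
| 10.5.2, 10.5.3, 10.5.5 laboratory, vital signs, ECG | by treatment group | by treatment group |
| 10.6.2 LVEF and stroke volume | tables and figures | none |
| 10.7 NT-proBNP | mean plots and listing | none |

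HFpEF is therefore treated as a reportable cohort for safety and drops out only of the response outputs. No section gives a reason.

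**Healthy subjects.** By 01 June 2018, a year before SAP v3.0, the protocol counts all 19 healthy cohorts as fully implemented, so early discontinuation did not truncate Parts A and B. Section 9.2.1 shows that their echocardiograms were read and speaks of the measurements as reported. Sections 10.6.2 and 11 plan no Part A or B echo summary. Protocol Section 2.7 cites stroke volume change at 5 and 30 mg in healthy volunteers as one of two bases for the Part C starting dose; the other is safety and tolerability.

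**Timing and access.** The discontinuation memo is dated 15 April 2019 and the SAP amendment 17 June 2019. Protocol Section 6.2.1.3.1 makes the dose-level reviews unblinded and lists echocardiograms among the data seen. Protocol Section 3.1 plans an unblinded review at the end of Part C dosing.

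**The case against.** The strongest reply is that this is a disclosed reduction. The version history, the Introduction and Section 11 all say that scope was cut for an abbreviated report. Sections 2 and 4.1.2 restate the protocol, and Section 11 lists the departures. Echo was not singled out: PK parameters, exploratory endpoints and concomitant medications were cut too. The study is descriptive and safety is primary. All of this stands, so the criticism is not one of concealment. It is that the choice between two parallel cohorts has no stated reason.

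The reply is also right on echo quality. Section 9.2.1 records concerns about the Part A and B data and better precision from the second lab, though it found no clinically meaningful inconsistencies. By-dose tables with six active subjects per cohort from the less precise source would add little, and they are not asked for here. The sentence in 9.2.1 can also be read as naming the data source rather than promising a table; that is a reason to reword it.

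Three stronger readings are tempting and should not be drawn:
- That results drove the choice. Protocol Section 10.3 does say "Amgen staff and their designees involved in the study will not be blinded", but the sentence goes on to limit release of assignments to cases of need. Nothing shows that those who chose HFrEF had seen HFpEF echo results by arm.
- That finished HFpEF reads are being withheld. Sections 9.2.1 and 10.6.2 speak of Part C as a whole, and neither HFpEF reads nor final HFpEF enrolment is documented.
- That nothing outside HFrEF will be shown. The plots in 10.6.1 are not limited to HFrEF and may include other groups, although they are not a change-from-baseline comparison with placebo.

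**Conclusion.** The point holds as a gap in the reporting plan. A retained secondary endpoint has change-from-baseline summaries for LVEF and stroke volume in one cohort: 20 of 192 planned subjects, or between 0% and 7.2% of the 166 subjects known at 01 June 2018, depending on the unstated split. Within HFrEF the diastolic measures and ventriculo-arterial coupling are also dropped. The percentages rest on planned or interim counts and would change with final enrolment; the missing rationale would not.

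The documents do not show selective reporting. They leave a reader unable to rule it out, because the choice came after discontinuation, unblinded review was built into the study, and HFpEF is omitted only from the response outputs. This should be corrected before the report is finalised. It does not affect the primary safety analysis.

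**What to change.** 1. In SAP Sections 10.6.2 and 11, add the same LVEF and stroke volume (MoD and LVOT) tables and figures by treatment group for HFpEF, from the Part C (BWIC) analysis data. The Part C schedule includes flow Doppler at every echo visit, so both stroke volume methods apply. If few HFpEF subjects have reads, give a subject listing and state the number.
2. For Parts A and B, do one of two things. Either give a short descriptive summary of LVEF and volumetric stroke volume from the ICON data, carrying the precision caveat from 9.2.1 and using Doppler stroke volume only where flow Doppler was scheduled (in oral Part B on Day 1 it was done pre-dose but not at 2 or 6 hours). Or state in 4.1.2 and 9.2.1 that these data are not summarised, and why.
3. Name the Parts and cohorts covered by the plots in 10.6.1, and reword 9.2.1 to agree with 10.6.2 and Section 11.

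The cost is a few more descriptive tables in the abbreviated report, possibly on small numbers (at most 15 active and 5 placebo in HFpEF as planned). The HFpEF outputs reuse specifications already written for HFrEF. No new data are needed.
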